10.2.1 Cost-effectiveness

A trial-based economic evaluations will be performed at 11 years after surgery (i.e. 1 year after RFU or COD at 10 years), separated for THA and TKA. Both economic evaluations will be performed for the primary outcome (PROMIS physical function) and for QALYs, and in accordance with the intention-to-treat principle. We will consider two perspectives: 1) healthcare perspective and 2) societal perspective. QALYs will be estimated by multiplying the patients' utility values by the duration for which they experienced a certain health state [25, 26]. Utility values will be based on the EQ-5D-5L, which health states will be valued using the Dutch tariff. All other kinds of resource utilization will be assessed using cost questionnaires administered at baseline, and 3, 6 and 12 months, and valued according to the "Dutch manual of costing" [27].

Missing data will be imputed using multivariate imputation by chained equations [28]. From the societal perspective, costs will include healthcare costs, absenteeism, presenteeism, unpaid productivity, and informal care costs. From the healthcare perspective, only costs accruing to the formal Dutch healthcare sector will be included. Costs will be assessed using cost questionnaires, and valued in accordance with the Dutch manual of costing. Cost and effect differences will be estimated using linear mixed models. It is very important to use mixed-model analyses, and hence to account for the possible clustering of cost and effect data (e.g., at the hospital level), as most economic evaluations fail to do so, whereas ignoring the possible clustering of data might lead to inaccurate levels of uncertainty and inaccurate point estimates. Incremental cost effectiveness ratios (ICERs) will be calculated by dividing

the difference in costs by that in effects. Bootstrapping techniques will be used to estimate the uncertainty surrounding the cost-effectiveness estimates (please note that non-parametric bootstrapping will be nested within the multiple imputation procedure). Uncertainty will be shown in cost-effectiveness planes and cost-effectiveness acceptability curves [29,30]. The latter indicate the probability of COD being cost-effective compared with RFU at different values of willingness to pay. Multiple sensitivity analyses will be performed to test the robustness of the cost-effectiveness results derived from the main analysis (e.g. complete-case analysis) [26].

For the budget impact analysis we plan to use the BIA tool as suggested and provided by ZonMw. The BIA will be based on the Dutch population, and hence Dutch incidence data will be used. Perspectives that will be considered are the societal, government (Budget Kader Zorg), and insurer perspective. Different scenarios will be evaluated including the following: 1) the intervention is not implemented, i.e. all patients will receive RFU only, 2) the intervention is offered to the whole patient population, i.e. all patients receive COD, and 3) the intervention is only offered to specific subgroups of the potential patient population, such as patients with the lowest risk of complications. These subgroups will be defined based on the results of the study, e.g. subgroups who particularly benefit from the intervention. The cost of the intervention mix will be valued using Dutch standard costs for the societal perspective, actual NZA tariffs for the government perspective, and average tariffs NZA for the insurer perspective.

This cost-effectiveness and budget impact analysis will comply with the 'Dutch guideline for economic evaluations in health care' [31].

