3. STUDY DESIGN

During the grant application process, all relevant stakeholders were involved in setting up this study protocol during a co-creation process. The co-creation team consisted of representatives from patient associations, healthcare insurers, the knowledge institute of the federation of medical specialists, the national healthcare institute, methodological and statistical expertise, the Netherlands Orthopaedic Association (NOV), the ZE&GG program for appropriate healthcare, and the project team. ZE&GG organized meetings to discuss crucial points with the stakeholders, which resulted in a well-considered research protocol approved by all involved stakeholders. The NOV signed a declaration of support and commits to implementation of the results.

In this study a randomized controlled trial with 3 arms will be performed. Patients will be randomized 1:1:1 in the following groups:

[figure not shown]
1. RFU: routine follow-up at 10 years after THA or TKA (control)
2. Active COD: No RFU at 10 years. Patients will be informed about the study and complete questionnaires. Check-ups are scheduled only on demand by the patient or health care professional (HCP) (intervention)
3. Passive COD: No RFU at 10 years. Patients will not be informed about the study to avoid any trigger to contact a HCP and will not complete questionnaires (intervention)

Patients will be followed for 1 year after RFU or COD (11 years after surgery). Informing the patients about the study and letting them complete questionnaires might result in trigger bias to contact a HCP. Therefore, patients in the intervention group will be divided into two groups: 1) one group will be informed about the study and complete questionnaires (active COD), 2) the other group will not be contacted and informed about the study to avoid trigger bias (passive COD). Of the latest group, only data from the LROI and EPD will be used. The control group will receive RFU at 10 years after THA or TKA and will complete questionnaires. Both groups completing questionnaires (active COD and RFU group) will be actively asked to participate in the study and to complete questionnaires and therefore will be randomized after informed consent.

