8.1.2 Secondary study parameters/endpoints (if applicable)

- PROMIS physical function
- Number and type of surgical interventions (like DAIR, partial component exchange, revision surgery (full prosthesis replacement), irrigation and debridement (without component retention))
- Additional healthcare consumption related to THA or TKA FU (like clinical visit, telephone consultations, X-ray, CT scan, MRI scan, laboratory tests)
- Costs (based on electronic patient records and additional questionnaires, including all visits to healthcare professionals outside the hospital)
- Numeric Pain Rating Scale (NPRS)
- Numeric Satisfaction Rating Scale (NSRS)
- Health related quality of life (EQ-5D-5L)

For the passive COD group only available data from the EPD and LROI will be collected.

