8.3 Study procedures

This study will be conducted in 10 Dutch hospitals across the Netherlands. Patients will be recruited using the LROI register and EPD. After inclusion, baseline characteristics will be obtained from the EPD and LROI register. Information on patient background will be collected to explore potential differences in follow-up needs, including among patients with different ethnic backgrounds. Previous research shows that people with a migrant background visit specialists and hospitals less often than native Dutch patients with similar health and SES [21]. Acknowledging the sensitivity of this topic, a 'prefer not to say' option is provided.

Patients will be scheduled for a clinical visit or not depending on the randomization group. The clinical visit contains of a check by the orthopaedic surgeon or orthopaedic resident and an X-ray. Additionally, a physical examination can be performed in case of concerns.

Information about the clinical visit will be collected. The patient or the HCP can also schedule a clinical visit in case of concerns, pain or symptoms. Information about these visits will also be collected.

Patients randomized to the active COD or RFU group will be asked to complete the questionnaires online or on paper. Completion time will be around 10-25 minutes. Table 1 depicts the data collection and assessments at baseline and during follow-up appointments.

Study data will be collected onto an electronic case report form (eCRF) in Castor EDC. The primary outcome will be measured at 11 years after surgery, i.e. 1 year after RFU or COD at 10 years. EQ-5D-5L and costs will be measured at 10 years after surgery (baseline), and at 3, 6, and 12 months after baseline in the RFU and active COD group. The other outcomes will be measured only at 10 years (baseline) and 11 years after surgery (end point).

Table 1: Overview of data collection and assessments.

	Baseline (10 years after surgery) (+/- 30 days)	In case of check-up on demand (10-11 years after surgery)	3 months (+/- 30 days)	6 months (+/- 30 days)	12 months (11 years after surgery) (+/- 30 days)
Clinical visit	X*	X			
Physical examination [#]	X	X			
X-ray	X*	X [#]			
Healthcare consumption	X	X	X	X	X
Questionnaires:**					
PROMIS	X				X
EQ-5D-5L	X		X	X	X
NPRS	X				X
NSRS	X				X
Costs	X		X	X	X

* Only RFU group

[#] In case of concerns

** Not for passive COD group

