In case of a clinical visit information will be collected about the visits, like whether the visit was a routine visit or on demand, the reason for the visit, date of the visit, consequences of possible findings (like change in policy and secondary health consumption). In case of a routine visit, we will collect data whether the patient cancelled the appointment and the reason of cancellation.

PROMIS physical function will be obtained using the short form (SF) [22]. In case hospitals already use computer adaptive testing (CAT) of PROMIS physical function in clinical practice, this will be used. Version 10b will be used. The SF PROMIS physical function consists of 10 questions and is expressed by raw summed score ranging from 10 to 50, which can be converted to a T-score and SE. The T-score is a standardized score with a mean of 50 and a SD of 10.

EuroQol-5D (EQ-5D-5L) is a general health-related quality of life questionnaire and consists of five questions regarding mobility, self-care, usual activities, pain/discomfort and anxiety/depression and one visual analog scale (VAS) to document the perceived quality of life [23]. The quality of life is described by 2 scores, the index value, which range from 0 to 1, and the VAS score, which range from 0 to 100. For both scores applies the higher the better. Numeric Rating Scale for pain (NPRS) is a scale ranging from zero to ten on which patients can score their pain [24]. It is a widely used instrument in varying populations due to its ease of administration and clinical relevance to the patient. The lower the score, the better.

Numeric Rating Scale for satisfaction (NSRS) will be measured by a single question: "How satisfied are you with the results of the treatment?" The patient will answer this question with a NRS scale ranging from zero to ten. The higher the score, the better.

Health consumption and costs will be measured using the EPD. Health consumption includes both the primary outcomes clinical visits and X-rays, as well as additional health care use, including telephone consultations and scans. The LROI register will be used to collect data about revision surgery. A questionnaire will be used to get more insight in the health consumption and costs which cannot be obtained from the EPD. This questionnaire is made in collaboration with a HTA expert and patient representatives.

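### Section 10.2.1 costs COD by questionnaires that passive COD never receives, so the objective on costs of informing patients has no analysis and the budget scenario's COD arm is unnamed

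*Protocol*

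**What the plan says.** **Cost source.** Protocol section 10.2.1 states "Costs will be assessed using cost questionnaires, and valued in accordance with the Dutch manual of costing". Section 8.1.2 defines the cost endpoint differently: "Costs (based on electronic patient records and additional questionnaires, including all visits to healthcare professionals outside the hospital". Section 8.3 says "Health consumption and costs will be measured using the EPD" and keeps the questionnaire for what the EPD cannot supply; revision surgery comes from the LROI.

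**Who is measured.** Section 8.3 collects EQ-5D-5L and costs at baseline and "at 3, 6, and 12 months after baseline in the RFU and active COD group". The footnote to the questionnaire block of Table 1, which includes PROMIS and costs, reads "Not for passive COD group". Section 8.1.2 adds: "For the passive COD group only available data from the EPD and LROI will be collected".

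**Why there is a passive arm.** Section 3 explains: "Informing the patients about the study and letting them complete questionnaires might result in trigger bias to contact a HCP". The passive group is left uncontacted for that reason.

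**What is to be answered.** A secondary objective in section 2 is the effect of informing patients about COD on complications, visits, surgery and costs. The second budget impact scenario in section 10.2.1 is that "the intervention is offered to the whole patient population, i.e. all patients receive COD". The section gives unit prices for each perspective but no source for the volumes of care.

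**The concern.** The protocol names a possible distortion of care-seeking and allocates a third of its patients to an arm meant to be free of it. The cost analysis it then describes cannot use that arm. This has two consequences.

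- The cost part of the objective on informing patients cannot be answered from questionnaires that the uninformed group never receives.
- National roll-out of COD would involve no study letter and no rounds of trial questionnaires. If the budget scenario takes its volumes from active COD, visits prompted by the trial would be counted as part of COD for the whole country. The direction would be against COD: its saving would look smaller than it is.

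**Working it through.** The plan gives no visit rate, unit cost or trigger size, so there is no figure of its own to reproduce. The first four steps compare the text; the last two are illustrations on stated assumptions.

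1. **Effect side of the ratio.** Section 10.2.1 uses PROMIS physical function and QALYs from EQ-5D-5L. Passive COD has neither (section 8.3, Table 1). The ratio is therefore RFU against active COD, whatever the cost source.

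2. **Cost side.** Section 10.2.1 names cost questionnaires. An earlier sentence there applies them to all other kinds of resource use, without saying what those are other than, and the EPD is not mentioned. Sections 8.1.2 and 8.3 use the EPD as well, with questionnaires filling the gaps. These statements differ, and the difference decides whether passive COD can have any cost data.

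3. **The objective on informing patients.** The three-group models in section 10.2 cover complications, clinical visits and surgical interventions (and patient-reported outcomes). Costs are not among them. Section 10.2.1 cannot supply them from questionnaires. No analysis in section 10 therefore answers the cost part of the objective, although hospital use of passive COD is collected from EPD and LROI.

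4. **Budget impact.** No arm is named as the source of volumes for the scenario in which all patients receive COD.

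5. **What a trigger effect would do.** Let RFU patients make 1 routine visit plus *r* on-demand visits a year, and passive COD patients *p* visits. Let study contact add *t* visits in active COD and *u* in RFU.
 - Saving without contact: 1 + r − p.
 - Observed saving: (1 + r + u) − (p + t).
 - Understatement: (t − u) / (1 + r − p).

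 Assumptions, none from the protocol: r = 0 to 0.1, p = 0.05 to 0.10. With u = 0:

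| t | Saving understated | Visit volume, active ÷ passive = (p + t)/p |
|---|---|---|
| 0 | 0% | 1.0 |
| 0.02 | 1.9–2.2% | 1.2–1.4 |
| 0.05 | 4.8–5.6% | 1.5–2.0 |
| 0.10 | 9.5–11.1% | 2.0–3.0 |
| 0.20 | 19.0–22.2% | 3.0–5.0 |

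 Example: r = 0, p = 0.10, t = 0.10 gives 0.10 / 0.90 = 11.1%. If RFU shares half the effect (u = t/2), each percentage halves; if it shares all of it (u = t), the understatement is zero. The last column does not depend on u, and a scenario that takes COD volumes from active COD would carry that factor.

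6. **Precision of active against passive COD.** With 250 per group for each joint (section 4.4) and a proportion π with a visit, the 95% half-width is 1.96 × √(2π(1 − π)/250). This is 0.038 at π = 0.05 and 0.053 at π = 0.10. A trigger effect of 0.02 would not be told apart from none, so showing both results is safer than relying on a test.

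**The case against.** Several arguments go the other way, and most of them stand in part.

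- **The budget scenario.** A reader might infer that the national estimate is built on active COD. The text does not say so. What it shows is an open source, not a wrong one.
- **Trigger bias.** A reader might infer that the protocol regards active COD as inflated. Section 3 says only that bias might result.
- **Use of passive COD.** A reader might infer that this arm is wasted. Section 10.2 compares visits, complications and surgery across all three groups, so any difference in visits between active and passive COD will be visible. The gap is confined to costs.
- **RFU patients are contacted too.** They complete the same questionnaires, so part of any trigger effect may cancel in the main comparison. Full cancellation is not assured, because a scheduled visit may absorb concerns that active COD patients have to raise on demand.
- **Active COD is the right main input.** Passive COD cannot give QALYs, a societal result or out-of-hospital costs. It is also not selected by consent (section 4.1 allows for 33% declining), so comparing it with consented arms mixes selection with the effect of contact. This stands.
- **Scenarios belong to a later plan.** The lists of sensitivity analyses and budget scenarios in section 10.2.1 are open, and a passive COD scenario would fit either. Its absence alone is no defect. But a later plan would still inherit a cost source that conflicts with two other sections and that rules out an objective of the protocol.

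**Conclusion.** The point holds in a limited form. As written, the cost-effectiveness ratio is RFU against active COD and should say so. The cost source in section 10.2.1 disagrees with sections 8.1.2 and 8.3. The cost part of the objective on informing patients has no analysis, although the hospital data for it will be collected. For the budget scenario, the finding is only that the arm is not named and that a trigger effect, if there is one, would enter through active COD.

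The size cannot be derived from the protocol. The 0% to about 22% range for the visit saving rests wholly on the assumed rates and on no effect in RFU; any sharing of the effect by RFU reduces it. It concerns visits, not euros, and is not scaled to the country, because the protocol does not give the national cohort left after the age, indication and bilateral-surgery criteria. The main randomised comparison is not called into question. This is a worthwhile clarification, not a serious flaw.

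**What to change.** Change section 10.2.1 in four places:

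1. State one cost source, consistent with sections 8.1.2 and 8.3: EPD and LROI for hospital use, questionnaires for the rest.
2. Name active COD as the COD arm in the ratio and in the main economic analysis, and name the arm that supplies volumes for each budget scenario.
3. Add a hospital-cost comparison of RFU, active COD and passive COD, with visits, X-rays and surgery taken from EPD and LROI in all three groups and valued at the same unit prices. Using one source in every arm avoids differences in ascertainment. This answers the cost part of the section 2 objective as far as hospital costs go.
4. Run the scenario in which all patients receive COD a second time with passive COD hospital volumes, and show it beside the active COD result.

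**Cost.** No new data collection; one further comparison and one further scenario for each joint. The downside is that the passive COD results cover hospital costs only and come from a group not selected by consent. The scenario should be labelled a sensitivity result, not a randomised estimate, and the three-group comparison should carry the same caution about consent.

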8.1.3 Other study parameters (if applicable)

- Patient characteristics (like age, gender, BMI, ASA score, ethnicity, employment status, home-hospital distance and educational level)

- Surgical information of primary arthroplasty (like surgery date, approach, type of prosthesis, fixation method, surgical duration, and intra-operative complications)
- Postoperative characteristics (like length of stay, in-hospital complications and discharge destination)
- Healthcare consumption, complications, and surgical interventions from the time of THA/TKA up to 10 years postoperatively

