10.2 Secondary study parameter(s)

For the secondary analysis, the aforementioned GLMM analyses on number and type of complications and clinical visits will be repeated comparing the 3 groups, namely the RFU, active COD and passive COD.

Secondary patient-reported outcomes, namely PROMIS physical function, NPRS, NSRS and EQ-5D-5L, will be presented as mean with standard deviation in case of normality or median and interquartile range otherwise. These parameters will be analysed using linear mixed models, with repeated measures clustered within participants and participants within

hospitals (random intercepts). Intervention group (RFU vs. active COD vs. passive COD), baseline score, and time (3, 6, 12 months) are included as fixed effects, to determine the crude effect of the intervention. To correct for possible confounders, baseline variables will be added to the model as fixed effects.

The total number of surgical interventions at 1 year follow-up (11 years after surgery) will be presented by median and interquartile range. The number of complications will be compared between 3 groups, namely the RFU, active COD and passive COD, using GLMM, with a Poisson distribution. A random intercept for the centre will be included in the model to account for clustering within centres. GLMM will also be used to correct for and to investigate the effect of possible confounders..

The type of surgical interventions at 1 year follow-up (11 years after surgery) will be presented categorically by numbers and percentages. The type of surgical interventions will be compared between 3 groups using GLMM with logistic regression, adjusting for possible confounders and incorporating centre as a random intercept.

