10.3 Other study parameters

Other study parameters, like patient characteristics and surgical information, will be given as numbers and percentages in case of categorical data. Continuous variables will be presented by mean and standard deviation in case of a normal distribution. In case of non-normality, median and interquartile range will be given. These parameters will be used to describe the included population and the clinical visits, but also to adjust the intervention effects.

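### Section 10.2.1 states no adjustment of QALY, PROMIS and cost differences for their baseline values, although these are collected and section 10.2 uses the baseline score

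*Protocol*

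**What the plan says.** Protocol section 10.2.1 describes the economic evaluation in some detail: two perspectives, the Dutch EQ-5D-5L tariff, chained-equation imputation, and bootstrapping nested in the imputation. On the estimation model it says "Cost and effect differences will be estimated using linear mixed models", and the reason it gives is clustering of cost and effect data, for example by hospital. It names no covariate. The two effect measures are PROMIS physical function and QALYs. On the latter, "QALYs will be estimated by multiplying the patients' utility values by the duration for which they experienced a certain health state".

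The baseline values exist. Section 8.3 states that "EQ-5D-5L and costs will be measured at 10 years after surgery (baseline), and at 3, 6, and 12 months after baseline", and Table 1 there shows PROMIS at baseline and 12 months. Section 10.2.1 itself refers to "cost questionnaires administered at baseline, and 3, 6 and 12 months".

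For the same instruments as clinical outcomes, section 10.2 is explicit: "baseline score, and time (3, 6, 12 months) are included as fixed effects". It continues: "To correct for possible confounders, baseline variables will be added to the model as fixed effects". Section 10.3 says of the other study parameters: "These parameters will be used to describe the included population and the clinical visits, but also to adjust the intervention effects". The list of those parameters in section 8.1.3 includes "Healthcare consumption, complications, and surgical interventions from the time of THA/TKA up to 10 years postoperatively".

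**The concern.** A one-year QALY computed from utilities at 0, 3, 6 and 12 months contains the baseline utility directly, and also indirectly, because later utilities correlate with it. A difference in baseline utility that arises by chance at randomisation therefore appears in part as a QALY difference unless the model conditions on baseline. Where baseline predicts outcome well, leaving it out also enlarges the standard error.

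This matters here for three reasons. Cost-effectiveness belongs to the primary objective in section 2. Section 1 expects that replacing routine follow-up will not compromise patient-relevant outcomes, so the QALY difference that forms the denominator of the ICER is expected to be small. And THA and TKA are analysed separately, so each comparison rests on its own, smaller sample.

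There is also a matter of consistency. PROMIS is baseline-adjusted in 10.2 and is an effect measure in 10.2.1 with no baseline term stated. Read literally, the trial could report two different PROMIS effects for the same patients. Baseline questionnaire costs are collected without a stated role in the analysis.

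**Working it through.** **Inputs from the protocol.** Assessments at 0, 3, 6 and 12 months (8.3). Comparison of RFU with active COD, since passive COD completes no questionnaires. 190 analysable patients per group, with 250 randomised, separately for THA and TKA (4.4, 10).

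**The plan's own figure.** With a 10% complication rate in both groups, a 10-point margin, a two-sided 95% interval and 80% power for equivalence: n = 2 × 0.10 × 0.90 × (1.960 + 1.282)² / 0.10² = 189.1, rounded up to 190. Also 250 × (1 − 0.24) = 190, so 250 randomised matches 24% loss, within the stated 20-25%. The 190 reproduces and is used below. The protocol gives no corresponding figure for QALYs or costs.

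**Assumptions.** The protocol gives no utility SD and no correlation between visits. I take an SD of 0.15 to 0.25 and an equal correlation ρ of 0.4 to 0.8 between all visits, with SD 0.20 and ρ 0.6 as the middle case.

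**Step 1: QALY weights.** Applying the trapezoid rule to intervals of 0.25, 0.25 and 0.5 year gives weights 0.125, 0.25, 0.375 and 0.25 for 0, 3, 6 and 12 months (sum 1).

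**Step 2: chance baseline difference.** SE = SD × √(2/190). For SD 0.20 this is 0.0205. Over SD 0.15 to 0.25 it is 0.015 to 0.026, a 95% range of ±0.030 to ±0.050.

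**Step 3: share carried into an unadjusted QALY difference.** Slope = 0.125 + 0.875ρ.

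**Step 4: variances in units of SD².** Unadjusted: 0.28125 + 0.71875ρ, where 0.28125 is the sum of the squared weights. Adjusted: the same minus slope².

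| ρ | Share carried | Unadjusted SE (SD 0.20) | Adjusted SE (SD 0.20) | Variance reduction |
|---|---|---|---|---|
| 0.4 | 0.475 | 0.0155 | 0.0120 | 40% |
| 0.6 | 0.650 | 0.0173 | 0.0111 | 59% |
| 0.8 | 0.825 | 0.0190 | 0.0086 | 79% |

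Middle case in full: the unadjusted variance is 0.28125 + 0.43125 = 0.7125, and the adjusted variance is 0.7125 − 0.65² = 0.29. Multiplying the square roots by 0.0205 gives 0.0173 and 0.0111. The reduction is 0.4225/0.7125 = 59%.

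**Step 5: carried amount in QALYs.** Middle case: 1.96 × 0.65 × 0.0205 = ±0.026 (95% range). Over all the assumptions the range is ±0.014 to ±0.042.

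**Sensitivity to n.** With all 250 per arm, the middle-case standard errors are 0.0151 unadjusted and 0.0096 adjusted. The proportionate gain is the same.

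**Costs and PROMIS.** No cost SD or correlation is given, so the gain for costs cannot be calculated. I have not quantified PROMIS, because 10.2.1 does not say whether its effect is a 12-month score or a change.

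**The case against.** The strongest objection is that silence is not a choice. The sentence on linear mixed models lists no fixed effects at all, not even treatment group, so it is not a complete model. Section 10.2.1 sits under 10.2, which adjusts the same two instruments for baseline score and adds further baseline variables. Section 10.3 says, without limiting it to one outcome, that the other parameters serve to adjust intervention effects, and earlier healthcare consumption is among them. Covariate lists for economic models are also often left to an analysis plan, which is not shown here.

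Much of this stands. A reader might infer that the protocol has decided on an unadjusted economic analysis, or that baseline costs will go unused. The text supports neither reading. The surrounding sections lean towards adjustment, but they do not reach the models in question. The baseline-score term in 10.2 belongs to a repeated-measures model of scores, not to a QALY. The list in 8.1.3 contains neither baseline utility nor the baseline cost questionnaire. And 10.2.1 goes into enough detail on imputation, bootstrapping and clustering that the missing baseline term leaves a real ambiguity.

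Three other strong readings also fail:

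- **Bias.** Under 1:1 randomisation a baseline imbalance is random error, and the planned bootstrap would reflect it.
- **Full carry-over.** The imbalance does not pass whole into the ICER. The share is 0.125 + 0.875ρ, below 1 for any ρ below 1.
- **Sign of the ICER.** Adjustment would not settle the sign. If the true QALY difference is near zero, the sign stays unstable with a standard error of 0.011 as well.

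**Conclusion.** The point holds as an improvement to the specification and not as a demonstrated error. Section 10.2.1 states no baseline adjustment for any of its three outcomes, while the section above it does so for two of the instruments and all the baselines are collected. Followed literally, the QALY comparison would carry 48% to 83% of a chance baseline utility difference. Its standard error would be about 0.017 where 0.011 is attainable (SD 0.20, ρ 0.6, 190 per arm), and the variance reduction forgone would be 40% to 79% over ρ from 0.4 to 0.8.

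These sizes rest on an assumed SD, an equal correlation between visits, and a trapezoid QALY that includes baseline utility. The direction of the result does not depend on the exact values, provided that baseline and later utilities are positively correlated. What is at stake is precision and robustness to chance imbalance.

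**What to change.** Add to section 10.2.1: 'QALY differences will be adjusted for baseline EQ-5D-5L utility, PROMIS differences for baseline PROMIS, and cost differences for baseline costs, as fixed effects in the linear mixed models, fitted within each imputed and bootstrapped sample.'

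This brings 10.2.1 into line with 10.2, gives the baseline cost questionnaire a defined use, and fixes the choice before results are known. It requires no extra patients, visits or questionnaires. The only cost is the wording change. If a separate health-economic analysis plan already says this, a cross-reference in 10.2.1 is enough.
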